**2. Data Collection:**

The electronic medical record and other Penn Medicine secondary databases used to collect data in routine care will be used to collect information on study participants. We will also collect data from the U.S. Census via publicly available datasets.

**Aim 1**

The primary outcome will be PRO adherence, measured at the patient level as the proportion of expected PRO questionnaires completed per patient. Secondary specifications will include:

- % patients completing at least one PRO questionnaire during study period
- % patients completing at least one PRO questionnaire per month during the study period

Secondary implementation outcomes will include:

- % patients with at least one note documenting PROs during study period
- % patients with at least one note documenting PROs per month during study period
- For Arms 2-3 only: time to alert response

Secondary effectiveness outcomes will include:

- Symptom burden, measured as a composite and for each PRO/symptom
  - a. For Arms 2-3 only: % patients who trigger alert
- Acute care utilization, measured as % patients with ED visit or hospitalization
- Treatment delays/modifications, measured as % patients with treatment delay/modification
- Duration of therapy

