### ABSTRACT

Routine monitoring of patient-reported outcomes (PROs) for patients with advanced solid malignancies is an evidence-based practice that improves symptoms and quality of life, reduces unplanned acute care, and extends overall survival. However, patient-level adherence and clinician-level adoption to PRO monitoring is suboptimal. We will conduct a three-arm randomized pragmatic trial to test the implementation and effectiveness of patient- and nurse-directed strategies to improve engagement in PRO monitoring across in-clinic and remote monitoring settings. Participants will include patients initiating systemic cancer treatment for solid malignancies at participating Implementation Laboratory sites within the Penn Implementation Science Center in Cancer Control. Eligible patients will be randomized independently to: (1) usual practice (i.e., encounter-based PRO administration via patient portal or tablet); (2) encounter-based PRO monitoring with patient reminders and nurse alerts; or (3) remote PRO monitoring with patient reminders and nurse alerts. The primary outcome will be PRO adherence, measured at the patient level as the proportion of expected PRO questionnaires completed per patient over a 3-month follow-up period. Secondary outcomes will include measures of clinical adoption of PROs, and patient health-related quality of life, duration of therapy, acute care utilization, and treatment delay/modification.

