## **OBJECTIVES:**

- (1) Evaluate the implementation and effectiveness of patient- and nurse-directed strategies across in-clinic and remote monitoring settings, using a three-arm pragmatic cluster RCT.
  - H1a: Nudges to patients and alerts to nurses will improve patient-level PRO completion and clinician-level PRO engagement
  
- (2) Evaluate moderators of implementation effects, using a quantitative evaluation of secondary data from the electronic health record, area-level data via geocoding, and clinician surveys.
  - H2a: The impact of nudges will be moderated by clinician, patient, and outer setting factors.
  - H2b: Baseline PRO adherence rates will differ by race, ethnicity, and socioeconomic status.
  - H2c: The nudge arms will not be significantly differentially effective across subgroups.

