**STUDY PROCEDURES:**

**1. Detailed Description:**

Eligible patients will be identified pragmatically using the criteria listed above, and will be independently randomized to study arms using a three-arm design. A description of the three study arms follows:

- (1) Usual practice.** This arm will consist of encounter-based PRO monitoring, in which patients have an opportunity to complete PRO questionnaires via patient portal in advance of clinical encounters or via tablet during clinical encounters. While clinicians will be encouraged to view and discuss PROs with patients during clinical encounters, they will not be prompted to do so in real-time, nor will there be alerts for escalating symptoms.
- (2) Encounter-based PRO monitoring plus patient reminders and triage nurse alerts.** This arm consists of usual practice (described above) plus the addition of patient reminders to complete PRO questionnaires and triage nurse alerts for severe symptoms. Patient reminders will be operationalized through the Epic patient portal. Triage nurse alerts will be routed to Epic symptom management pools in response to a patient reporting moderate or severe symptoms. Patients will have the opportunity to decline or opt-out of triage nurse support. Clinical interventions stemming from triage nurse alerts will be up to the discretion of clinical teams – ie, clinical responses will be neither prescriptive nor mandatory. Notably, the entry point for triage nurse alerts (ie, Epic symptom management pools), as well as resultant clinical responses, are existing standard operating procedures/practices for patients reporting symptoms by phone.
- (3) Remote PRO monitoring plus patient reminders and triage nurse alerts.** This arm will consist of weekly PRO questionnaires administered via the patient portal, de-linked from clinical encounters. Patient reminders and triage nurse alerts will be operationalized as described in Arm (2).

We will use rapid cycle approaches (RCA) to optimize implementation strategies to ensure face validity and maximum effect. We will focus on optimizing content, messaging, and design. RCA procedures will involve design meetings with study team, discussions with administrators and clinicians who are members of our Implementation Lab, as well as piloting of nudges with potential participants to elicit feedback.

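### The two note-documentation outcomes set no limit on who wrote the note, so charted nurse responses to alerts, which only Arms 2 and 3 can generate, could count as clinician engagement

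*Combined protocol and SAP*

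**What the plan says.** Under Data Collection, Aim 1, the secondary implementation outcomes are the percentage of "patients with at least one note documenting PROs during study period", the percentage of "patients with at least one note documenting PROs per month during study period", and time to alert response, the last for Arms 2 and 3 only. The protocol does not say which authors, note types or encounters qualify, or how PRO documentation in a note will be identified.

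The construct behind these outcomes is stated twice. The Abstract says "Secondary outcomes will include measures of clinical adoption of PROs". H1a under Objectives reads "Nudges to patients and alerts to nurses will improve patient-level PRO completion and clinician-level PRO engagement".

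The arms differ in how PRO answers reach nurses (Study Procedures, Detailed Description). For Arm 1, the text says of clinicians that "they will not be prompted to do so in real-time, nor will there be alerts for escalating symptoms". For Arm 2, "Triage nurse alerts will be routed to Epic symptom management pools in response to a patient reporting moderate or severe symptoms", and Arm 3 uses the same mechanism. Appendix 1 adds a closing question, sent to Arms 2 and 3 only, asking whether the patient wants the triage nurse team to make contact about the symptoms just reported.

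The Statistical Analysis section compares binary secondary outcomes across arms with logistic models at a two-sided alpha of 0.05.

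**The concern.** Time to alert response cannot be compared with Arm 1, so the clinician half of H1a rests on the two note outcomes. As worded, they accept a note by anyone on the care team. The intervention creates a new occasion for nurses to write about a PRO, and it does so only in Arms 2 and 3. Carrying out the intervention could then register as its effect.

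An arm difference on these outcomes could mean that treating clinicians used PROs more, that triage nurses charted the alerts they handled, or both. The planned analysis cannot tell these apart. The stake is the reading of the implementation result. The primary outcome, PRO adherence, and the patient half of H1a are not touched.

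**Working it through.** **No plan figure to reproduce.** Power and Sample Size covers patient-level adherence only. No expected rate is given for the note outcomes, for alerts or for charted responses.

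**Step 1: routes to a qualifying note**

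| Route | Arm 1 | Arms 2 and 3 |
|---|---|---|
| Treating clinician writes about a PRO | possible | possible |
| Nurse handles a PRO-triggered alert and charts it, citing the PRO | no alerts | possible |
| Nurse handles a symptom call by phone | existing practice | existing practice |

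The third route does not start from a questionnaire, so it does not balance the second.

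**Step 2: size of the artefact.** Both inputs are assumptions:

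- c: share of patients with a treating-clinician note documenting PROs, set equal in all arms (no true effect).
- q: share of Arm 2 or Arm 3 patients with a charted nurse response citing the PRO. The Arm 1 equivalent is taken as zero; any such notes in Arm 1 would shrink the difference.

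If the two kinds of note are independent, the intervention-arm rate is 1 − (1 − c)(1 − q), and the spurious difference from Arm 1 is

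[1 − (1 − c)(1 − q)] − c = (1 − c)q.

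| | q = 10% | q = 20% | q = 30% |
|---|---|---|---|
| c = 20% | 8 points | 16 points | 24 points |
| c = 30% | 7 points | 14 points | 21 points |
| c = 40% | 6 points | 12 points | 18 points |

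**Step 3: dependence on overlap.** Independence is doubtful, because both notes need a completed questionnaire and patients with worse symptoms may attract both. Without independence, the difference lies between max(0, q − c) under full overlap and min(q, 1 − c) under none. At c = 30% and q = 20% this is 0 to 20 points, with 14 under independence. Positive overlap lowers every figure in the table.

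**Step 4: chance of a false finding.** The target of about 480 patients at 1:1:1 gives 480 / 3 = 160 per arm. I used a two-proportion normal approximation with a pooled variance under the null, as a stand-in for the logistic model:

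P(significant) ≈ Φ[(Δ − 1.96·SE₀) / SE₁].

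For c = 40% and q = 20%, the rates are 0.40 and 0.52:

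- Δ = 0.12
- SE₀ = √(2 × 0.46 × 0.54 / 160) = 0.0557
- SE₁ = √((0.40 × 0.60 + 0.52 × 0.48) / 160) = 0.0553
- Φ[(0.12 − 0.1092) / 0.0553] = Φ(0.195) ≈ 58%

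The same formula gives 19% at q = 10% and 90% at q = 30%, against a nominal 5%. These figures also rest on independence.

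**The case against.** The strongest reply is that the key step is not in the documents. They do not say that nurses write a note when they handle an alert, or that the note would cite the PRO. Clinical responses are left to the team's discretion, patients may decline nurse support, and time to alert response need not be taken from a note. This stands. A reader might infer that the outcome is certainly contaminated, but the text supports only that it can be.

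A second reply is that nurses are clinicians. The term is never defined, H1a itself pairs nurse alerts with clinician engagement, and the Background lists weak links between reported symptoms and clinical response as a problem to be solved. On that view a charted nurse response is the intended effect. Other usage points the other way. The Background lists clinician engagement as a separate limitation. The Arm 1 description has clinicians discussing PROs at visits. The clinician-level data for Aim 2 are years in practice and panel size. The ambiguity is real. Even on the sponsor's reading, the outcome merges two behaviours, and H1a comes close to saying that alerting nurses leads nurses to answer alerts.

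Two stronger readings are tempting and should be resisted:

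- A reader might infer that weekly questionnaires give Arm 3 more alerts than Arm 2, so that this comparison is distorted in a known direction. Arm 3 has more occasions, but it relies on the portal while Arm 2 keeps the in-clinic tablet. Completion could be lower in Arm 3, and the outcome needs only one note. The direction is not established.
- A reader might conclude that only visit notes should count. Arm 3 is deliberately separated from visits, so that rule could discard genuine between-visit use and understate adoption in the remote arm.

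**Conclusion.** The point holds in a limited form. As worded, both note outcomes can rise in Arms 2 and 3 without any change in treating-clinician behaviour, because an alert-driven nurse note would qualify and Arm 1 has no alerts. Whether this happens, and how often, cannot be read from the documents. The illustrative 14 points (0 to 20 depending on overlap) at c = 30% and q = 20% shows that the effect could matter; it is not an estimate.

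One limit remains after any change of author rule. A note can document a PRO only if one was completed, so better completion alone may raise the note rate. Separating authors does not remove that.

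This is a cheap improvement to secondary outcomes, held with medium confidence.

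**What to change.** In all three arms, compute both note outcomes by author role, and state how a note is judged to document PROs.

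- **Measure for the clinician part of H1a:** notes by the treating oncology physician or advanced practice provider, from any encounter type, including between-visit contacts.
- **Reported separately, Arms 2 and 3 only:** triage-nurse alert-response notes, as a measure of intervention delivery.
- **Supplementary:** the any-author version, so that no data are lost.

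The cost is an author-role field in the EHR extract and a few sentences of outcome definition. The downside is a lower outcome rate and probably a smaller effect on the measure that carries the claim.

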### INTRODUCTION

Routine monitoring of patient-reported outcomes (PROs) for patients with advanced solid malignancies is an evidence-based practice that improves symptoms and quality of life, reduces unplanned acute care, and extends overall survival. Still, there is variation in adoption of and adherence to routine PRO monitoring, owing to multilevel barriers to implementation and concerns among clinicians regarding the utility of PROs in actual practice. While high levels of patient adherence to PRO monitoring have been reported in clinical trials, real-world adherence is

suboptimal. Our preliminary research shows that in a large, multi-site rollout of PROs, patient-level adherence was less than 50 percent, with patients from racial and ethnic minority groups even less likely to complete PRO questionnaires and more likely to report uncontrolled symptoms. Moreover, only half of Penn medical oncologists report that routine PRO monitoring is useful in practice. There is critical need to develop, test, and disseminate strategies to improve patient-level PRO adherence to ensure optimal and equitable symptom management, quality of life, and survival for patients with advanced cancer.

Implementation strategies informed by behavioral economics are ideally suited to address this challenge, as it is fundamentally one of clinician and patient behavior change. For PRO monitoring programs to succeed in transforming cancer care, patients must longitudinally complete PRO questionnaires and clinicians must use the resultant patient-reported data in clinical decision-making. Clinician engagement and use of PRO data begets patient engagement, in part by signaling an approved behavior (injunctive norm) to which patients desire to conform. Repeated feedback is important for sustaining other health-promoting behaviors such as medication adherence. In particular, gamification strategies, which harness game design elements and patient heuristics to motivate behavior change, have shown promise. However, little research has harnessed these insights to promote longitudinal PRO adherence.

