### 2. ***Key Eligibility Criteria:***

#### *Key inclusion criteria*

Eligible patients must meet the following criteria:

- Initiate a new line of systemic cancer therapy (ie, intravenous chemotherapy or immunotherapy) at a participating Implementation Lab site

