### **5. Statistical Analysis:**

#### **Aim 1**

The design is a three-arm randomized trial, resulting in three independent study arms: (1) usual practice, (2) encounter-based PRO monitoring with patient reminders and triage nurse alerts, (3) remote PRO monitoring with patient reminders and triage nurse alerts. Implementation and effectiveness outcomes will be assessed across arms. The main comparison for the purposes of power calculations will be Arm 2 vs Arm 1. Multivariable linear regression will be used to model patient PRO adherence as a function of nudge exposure (i.e., study arm assignment). Covariates will be assessed across study arms and included in the model if unbalanced across arms.

Significance will be determined using the z-score corresponding to each of the estimated effects, using a two sided type 1 error of 5%. All enrolled patients will be included in the intention-to-treat analysis.

The secondary outcomes will be similarly modeled except using logistic models as appropriate for binary outcome variables. All hypothesis tests will use a two-sided alpha of 0.05 as the threshold for statistical significance.

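### Acute care utilization counts planned as well as unplanned hospitalizations and has no stated rule for deaths, so it is a broader measure than the unplanned acute care in the rationale (minor; secondary outcome)

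*Combined protocol and SAP*

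**What the plan says.** The only definition is in STUDY PROCEDURES, 2. Data Collection, Aim 1, among the secondary effectiveness outcomes: "Acute care utilization, measured as % patients with ED visit or hospitalization". It does not separate planned from unplanned admissions, and death is not among the listed outcomes.

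The Abstract and the Introduction both say that routine PRO monitoring "improves symptoms and quality of life, reduces unplanned acute care, and extends overall survival". The Abstract's list of this trial's own outcomes says only acute care utilization: "Secondary outcomes will include measures of clinical adoption of PROs, and patient health-related quality of life, duration of therapy, acute care utilization, and treatment delay/modification".

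The eligibility criterion is "Initiate a new line of systemic cancer therapy (ie, intravenous chemotherapy or immunotherapy) at a participating Implementation Lab site". Key Eligibility Criteria sets no stage limit and does not exclude patients with surgery or inpatient treatment already scheduled.

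For analysis, 5. Statistical Analysis, Aim 1 says: "The secondary outcomes will be similarly modeled except using logistic models as appropriate for binary outcome variables". It adds: "All enrolled patients will be included in the intention-to-treat analysis". No section says how a death during follow-up enters any outcome.

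**The concern.** The Detailed Description routes alerts to triage nurses when a patient reports moderate or severe symptoms. That route could plausibly prevent an ED visit or an unplanned admission. It has no evident way of preventing an elective operation or an admission scheduled to give therapy. Such admissions add events to both arms that the intervention cannot change.

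Death raises a separate question. With every enrolled patient in the denominator and a binary outcome, a patient who dies early without an ED visit or admission is counted with those who needed no acute care, which is the favourable category. The Abstract and Introduction speak of advanced solid malignancies, so some deaths within 3 months are foreseeable.

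At stake is how one secondary outcome is read. STUDY DESIGN describes a hybrid type 2 design in which effectiveness is evaluated alongside implementation, and this is the only listed effectiveness outcome that counts ED visits or admissions.

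**Working it through.** **Figures in the plan.** The documents give no event rate, effect size or power for this outcome, so there is nothing to reproduce. The calculations below are illustrations.

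**Inputs from the documents.** About 480 patients (Power and Sample Size) randomized 1:1:1 (STUDY DESIGN) gives 480/3 = 160 per arm. Alpha is 0.05 two-sided (Statistical Analysis).

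**Assumed inputs.** Unplanned-event risk is c in control and t in the intervention arm. A proportion q of patients in each arm has a planned admission, independent of unplanned events.

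**Planned admissions.** The risk of any event is C = 1 − (1 − c)(1 − q) in control and T = 1 − (1 − t)(1 − q) in the intervention arm, so C − T = (1 − q)(c − t). Power for two proportions is Φ[(|C − T| − 1.96·se0)/se1], with se0 = √(2p̄(1 − p̄)/160), p̄ = (C + T)/2 and se1 = √([C(1 − C) + T(1 − T)]/160).

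Worked case, c = 0.30, t = 0.225 (a 25% relative reduction), q = 0.10:
- C = 1 − 0.70 × 0.90 = 0.370 and T = 1 − 0.775 × 0.90 = 0.3025.
- The difference is 0.0675 and the relative risk is 0.3025/0.370 = 0.82.
- se0 = 0.0528 and se1 = 0.0527.
- Power = Φ[(0.0675 − 1.96 × 0.0528)/0.0527] = Φ(−0.68) = 25%.

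| Assumed unplanned risk | Planned q | Any-event risk | Risk difference (points) | Relative risk | Power |
|---|---|---|---|---|---|
| 30% vs 22.5% | 0 | 30.0% vs 22.5% | 7.5 | 0.75 | 33% |
| | 5% | 33.5% vs 26.4% | 7.1 | 0.79 | 28% |
| | 10% | 37.0% vs 30.3% | 6.8 | 0.82 | 25% |
| | 15% | 40.5% vs 34.1% | 6.4 | 0.84 | 22% |
| 30% vs 18% | 0 | 30.0% vs 18.0% | 12.0 | 0.60 | 71% |
| | 5% | 33.5% vs 22.1% | 11.4 | 0.66 | 62% |
| | 10% | 37.0% vs 26.2% | 10.8 | 0.71 | 55% |
| | 20% | 44.0% vs 34.4% | 9.6 | 0.78 | 42% |

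For 30% versus 18%, the odds ratio moves from 0.51 to 0.56, 0.60 and 0.67. With a 25% relative reduction and q rising from 0 to 15%, power falls from 22% to 13% at 20% control risk, and from 47% to 33% at 40%.

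**Deaths without a visit.** Let m_c and m_t be the proportions dying without an ED visit or admission. As listed, the risk difference is c − t. If these deaths are counted as events it is (c + m_c) − (t + m_t), so the two differ by m_c − m_t.
- Equal proportions: at 1% per arm, 30.0% vs 22.5% becomes 31.0% vs 23.5%; at 5%, it becomes 35.0% vs 27.5%. The difference is 7.5 points throughout.
- A 2-point imbalance (0.02 × 160 = 3.2 patients) moves the difference by 2 points. Under the default scoring this favours the arm with more such deaths.

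**The case against.** The strongest reply is that the documents do not contradict themselves. The only Aim 1 hypothesis is "Nudges to patients and alerts to nurses will improve patient-level PRO completion and clinician-level PRO engagement". The phrase "reduces unplanned acute care, and extends overall survival" describes published benefits of PRO monitoring, and the trial's own outcome lists say acute care utilization without qualification. A reader might infer that the trial set out to reduce unplanned acute care and then failed to measure it. The documents do not support that: the reduction is cited rationale, and the measure still captures ED visits and unplanned admissions. This part of the reply stands. The outcome is diluted but remains usable.

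The reply can add that randomization balances planned admissions in expectation, so the cost is dilution and lost power, with no tendency to create a false effect. It can also say that counting every admission needs no judgement about admission type, which suits a pragmatic trial run from the medical record. Both points are fair, and they are reasons to keep the listed outcome.

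On death, a reader might infer that the plan scores deaths as successes and could thereby hide or reverse a harm. No section states such a rule; the scoring is only the default when nothing is said. A distortion needs an imbalance between arms in visit-free deaths, for which the documents give neither a rate nor a mechanism. Safety oversight does not rest on this outcome either. The Data Safety and Monitoring Plan has serious adverse events reviewed in real time and adverse events reported to the DSMB at least twice a year.

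What the reply leaves open is how planned admissions and deaths are to be treated when this outcome is interpreted.

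**Conclusion.** The point holds as a minor one about a single secondary outcome. The definition is broader than the unplanned acute care in the rationale, and nothing is said about deaths.

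The direction of the dilution follows from two assumptions: planned admissions are balanced across arms and independent of unplanned ones. Its size cannot be established from the documents. In the illustrations with a 25% relative reduction at 30% control risk, 5% to 15% planned admissions cost about 5 to 11 points of power that is low to begin with. With the larger assumed effect (30% versus 18%), 5% to 20% planned admissions cost about 9 to 29 points. How common planned admissions are in this population is unknown. The missing death rule affects the risk difference only to the extent that visit-free deaths differ by arm. The primary outcome is untouched.

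**What to change.** Keep the outcome as listed. Power and Sample Size reports in the past tense that enrollment ran ahead of expectation, so replacing a listed outcome would redefine it after accrual had begun.

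Before results are compared by arm, add to the Aim 1 outcome list:

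- A pre-specified analysis of the percentage of patients with an ED visit or an unplanned hospitalization within 3 months of enrollment. Use the admission type in the electronic record to exclude elective surgical admissions and admissions to give treatment, and write the rule down in advance.
- All-cause death within 3 months, reported by arm.
- As a companion, the percentage with an ED visit, an unplanned hospitalization or death within 3 months.

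The cost is small: a written rule and extra tables from the routine data sources the plan already uses, with no change to treatment, visits or the primary outcome. That the record holds a usable admission-type field and reasonably complete deaths is an assumption to confirm. Some admissions will be misclassified and some deaths may be missed, which is a further reason to report the any-hospitalization outcome alongside.
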